Blood samples (FBC, U&Es, LFTs, ACTH, DRC, PAC) will be taken prior to the second PET-CT scan. In the event that no abnormal findings were recorded after the first scan, patients will be observed for up to four hours following the second scan, and then discharged with no requirement for admission to the CLRF or an additional SST.

Procedures: End of trial

Healthy volunteers will conclude their involvement in the trial after their final assessment has demonstrated normal adrenal function. In the extremely unlikely event that an abnormality persists, the participant will continue to be monitored within the trial until one of the following conditions is met:

- Adrenal function returns to baseline, as determined by follow-up SST.
- Participant remains clinically stable,

and where further follow-up can be managed safely in the outpatient setting.

- An alternative cause for the adrenal dysfunction is identified.
- Participant is lost to follow-up.

Upon which their involvement in the trial will end.

Patients will conclude their involvement in the trial after the second [¹⁸F]CETO PET-CT scan. However, any patient with abnormal adrenal function test results following the first scan will not undergo a second PET-CT scan. Instead, they will continue to be monitored within the trial until one of the following conditions is met:

- Adrenal function returns to baseline, as determined by follow-up SST.
- Patient remains clinically stable, and where further follow-up can be managed safely in the outpatient setting.
- An alternative cause for the adrenal dysfunction is identified.
- Patient is lost to follow-up

Upon which their involvement in the trial will end.

Procedures for safety monitoring during trial

Automatic trial stopping criteria will be met if a single participant experiences any serious adverse reaction (i.e. a serious adverse event considered at least possibly related to the IMP administration). Stopping criteria will additionally apply if any severe non-serious adverse reactions (ARs) develop in two participants, independent of whether or not these are within the same system-organ-class. The following will then occur:

- The trial will be halted via a substantial amendment to the MHRA.
- No further dosing or recruitment will be undertaken
- A safety review by the Data Monitoring Committee (DMC) will be conducted to determine how to proceed with the trial
- Any patients who have their dosing

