9.6 Trial Outcome Measures

9.6.1 Primary outcome Measure

• The primary outcome measure is the overall safety of [¹⁸F]CETO. This will be assessed according to the frequency of adverse events, serious adverse events, clinically significant changes in vital signs, ECG and laboratory parameters.

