10.3 Participant Withdrawal Criteria

A participant can decide to withdraw from the trial at any time without further explanation. Participants may be removed from the trial at their choice or at Investigator's discretion if it is felt to be clinically appropriate. Reasons for participant withdrawal will be recorded in the Case report form (CRF). The participant will be reassured that their future care will not be affected by their withdrawal, and that their relationship with their responsible physician remains unaltered. The participant will be informed that any of their study data already stored will be retained, and will be used, if necessary, in the evaluation of the study drugs and for adherence to the relevant regulatory requirements.

Any participants who have their dosing discontinued will be withdrawn from the trial (as described in Section 11.5 Ongoing Safety Review). Withdrawal from the trial will also occur in the event of participant pregnancy. Healthy volunteers will be withdrawn from the trial in the event that they are taking medication at the point of [18F]CETO administration.

11 Trial Treatments

For the purpose of this trial, the radiopharmaceutical [¹⁸F]CETO, administered intravenously, is considered a Investigational Medicinal Product (IMP).

Oral dexamethasone is considered as a Non- Investigational Medicinal Product (nIMP) within this trial and will be supplied by local site's own stock, using standard labels and packaging.

The investigator is responsible for ensuring that deliveries of [¹⁸F]CETO and other study materials are safely and properly received, recorded, handled, and stored in accordance with all applicable regulatory guidelines, and used in accordance with this protocol. This responsibility may be delegated to appropriately trained personnel.

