13.1.6 Reference Safety Information (RSI)

A list of medical events that defines which reactions are expected for the IMP within a given trial and thus determining which Serious Adverse Reactions (SARs) require expedited reporting.

For this trial the Reference Safety Information is: located in the most recent version of the Investigator's Brochure for the PET Radiopharmaceutical [¹⁸F]CETO approved by the MHRA for use in this trial.

Due to the absence of any previous human data for [¹⁸F]CETO, all events will be considered unexpected. Therefore, all SARs in the trial will meet the unexpected criteria and will be reported as SUSARs.

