16.4 Criteria for the premature termination of the trial

The safety data and PET-CT data will be reviewed by the DMC following injections of [18F]CETO in the first 3 participants to provide an initial evaluation of [18F]CETO safety, and confirm the trial is able to proceed.

Furthermore, automatic trial stopping criteria will be met if a single participant experiences any serious adverse reaction (SAR, i.e. a serious adverse event considered at least possibly related to the IMP administration). Stopping criteria will additionally apply if any severe non-serious adverse reactions (ARs) develop in two participants, independent of whether or not these are within the same system-organ-class. The following will then occur:

- The trial will be halted via a substantial amendment to the MHRA.
- No further dosing or recruitment will be undertaken
- A safety review by the DMC will be conducted to determine how to proceed with the trial
- Any patients who have their dosing discontinued as a result of a SAR or a severe nonserious AR will be withdrawn from the trial
- Re-initiation of the trial can only be considered after MHRA approval via a substantial amendment. Any concurrently active participants will be re-consented before further IMP doses are administered, and all completed participants will be informed of the SAR or severe non-serious ARs.

Finally, if there is no demonstrable [¹⁸F]CETO uptake into human adrenal tissue in the first 4 participants (either healthy volunteers and/or patients), the trial will be halted and the DMC will be asked to consider if the trial should be stopped.

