16.5 Procedure to account for missing or spurious data

For participants who wish to withdraw entirely from the study, existing data acquired to the point of withdrawal will be included in the final study analysis, with missing data handled according to standard missing data methods, including missing-at-random methods.

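### Ending dosing after a serious or severe reaction is equated with leaving the trial, so later safety data in those patients can go uncollected

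*Protocol*

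**What the plan says.** - **Stopping criteria (16.4, repeated in 12.5 and the synopsis).** A criterion is met by one serious adverse reaction (SAR), or by severe non-serious adverse reactions (ARs) in two participants. The consequences listed include a trial halt, a review by the data monitoring committee (DMC), and this: "Any patients who have their dosing discontinued as a result of a SAR or a severe nonserious AR will be withdrawn from the trial".
- **Withdrawal (10.3).** The rule is worded more widely: "Any participants who have their dosing discontinued will be withdrawn from the trial". It refers to an ongoing safety review in section 11.5, but the text with that title is in 12.5. Of a withdrawn participant it says that "any of their study data already stored will be retained". It does not mention collecting anything further.
- **Abnormal SST after the first scan (synopsis, End of trial; also 12.5 and 12.7).** The second scan is not done. "Instead, they will continue to be monitored within the trial until one of the following conditions is met", and four end conditions follow.
- **Primary outcome (9.6.1).** Safety is judged by "the frequency of adverse events, serious adverse events, clinically significant changes in vital signs, ECG and laboratory parameters".
- **Serious reactions (13.1.6).** "all SARs in the trial will meet the unexpected criteria and will be reported as SUSARs".
- **Missing data (16.5).** "For participants who wish to withdraw entirely from the study, existing data acquired to the point of withdrawal will be included" in the final analysis, with "missing data handled according to standard missing data methods, including missing-at-random methods".

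**The concern.** Safety is the primary objective of this first-in-human trial. Patients who react badly to the first dose are the most informative participants, yet the protocol takes them out of the trial and does not say that anyone goes on measuring them. Two patients may both lose the second dose for a safety reason and be treated in opposite ways: one is followed to a defined end, the other leaves.

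At stake is what happens after the reaction: whether it resolves, whether laboratory or ECG changes appear later, and whether new events occur. The DMC needs that information for the review that the same list of consequences calls for. An analysis plan cannot recover data that were never collected.

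**Working it through.** The protocol gives no figure to reproduce: section 16.1 states that there was no power calculation. The check is mainly a comparison of sections.

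**1. Does withdrawal remove the event from the primary outcome?** Inputs from 16.3 and 11.1.1.5: up to 5 healthy volunteers with one dose each and 6 patients with up to two. That is 5 + 6 = 11 participants and at most 5 + 2 × 6 = 17 administrations. Suppose 1 or 2 patients react after the first dose and are withdrawn:

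| Reactors withdrawn | Participants with event | Exact 95% CI | Administrations |
|---|---|---|---|
| 1 | 1/11 = 9.1% | 0.2% to 41.3% | 17 − 1 = 16 |
| 2 | 2/11 = 18.2% | 2.3% to 51.8% | 17 − 2 = 15 |

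The reaction comes before the withdrawal, so it is recorded and counted. Withdrawal does not change the proportion.

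**2. What does the schedule (12.6) leave for a patient who reacts after scan 1?**

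| Situation | Assessments still scheduled |
|---|---|
| Withdrawn on the scan day | None required. The next-morning vital signs, blood tests and SST are no longer called for |
| Next-morning SST normal, no second scan | None. After scan 1, adverse event assessments are marked only at the SST follow-up visit (abnormal SST only) and at the repeat scan; the next ECG is also at the repeat scan |
| Next-morning SST abnormal | Follow-up visit with SST, blood tests, examination and adverse event assessment, if the patient is still in the trial |

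Section 12.7 ends a patient's participation after the second scan or, following an abnormal result, after adrenal follow-up. It has no branch for a patient with a normal SST and no second scan.

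**3. Do the two rules collide?** If the abnormal SST is itself classed as a SAR, or as a severe AR once the criterion is met, 10.3 and 16.4 withdraw the patient. For the same patient, 12.5, 12.7 and the synopsis require continued observation in the trial. Neither set of text gives way to the other.

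**4. Is there another route to the later data?** For SARs, partly. All are handled as SUSARs, and 13.6.2.1, 13.6.2.2 and 13.6.3.2 provide for follow-up information. That is case reporting, not scheduled vital signs, ECG and laboratory tests, and 13.6.3.2 leaves follow-up of long-term outcome optional. No such route is written for severe non-serious ARs.

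**5. How often could the stopping criteria be met?** The protocol gives no rates, so these are assumptions. With rate p per participant and all 11 dosed, P(at least one SAR) = 1 − (1 − p)^11 and P(at least two with a severe AR) = 1 − (1 − p)^11 − 11p(1 − p)^10.

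| Assumed p | At least one SAR | At least two with a severe AR |
|---|---|---|
| 1% | 10.5% | 0.5% |
| 5% | 43.1% | 10.2% |
| 10% | 68.6% | 30.3% |
| 20% | 91.4% | 67.8% |

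These show how readily a halt could occur. They overstate how often follow-up is lost, because a reaction in a healthy volunteer leaves no dose to discontinue.

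**The case against.** The case on the other side is substantial.

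- The event that triggers withdrawal is counted, and the primary outcome names frequencies and clinically significant changes, not duration or recovery.
- In 16.4 the rule operates only once a stopping criterion is met. The whole trial is then halted and reviewed by the DMC.
- SARs have their own follow-up reports.
- Little scheduled data is at risk. Each participant is observed for about 24 hours after the first dose and has a next-day SST. After a second dose there is none left to discontinue.

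All of this stands and limits the point. It does not supply an instruction to go on assessing a withdrawn reactor, and it does not settle which rule governs an abnormal SST that is itself the reaction.

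A reader might infer two stronger claims. The first is that the primary event frequency is truncated in those who have the event. Step 1 of the working shows that it is not. The second is that second-dose safety results will be imputed from patients who tolerated the first dose. The documents do not support this. Section 16.5 is limited to participants who themselves wish to leave entirely, which a withdrawal imposed by the protocol is not, and section 16.1 plans only summary statistics for safety. No section proposes a safety value for a dose that was never given.

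**Conclusion.** The point holds as a gap in data collection and an unreconciled pair of rules. The withdrawal text joins two separate decisions, giving no more tracer and collecting no more data, and the schedule and end-of-participation text provide nothing for a reactor with a normal SST.

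Its size is limited. At most 6 of 11 participants have a second dose to lose, each being 1/6 = 17% of the possible second administrations. The event count is unchanged. The loss is of later findings and of the course of the reaction, most clearly for severe non-serious ARs. Section 16.5 adds a smaller weakness: it names missing-at-random methods without excluding safety outcomes, and it gives no rule for withdrawals that the protocol imposes.

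This rests on reading withdrawal from the trial in its ordinary sense, as the end of trial assessments. If the sponsor intends follow-up to continue, the protocol should say so. The change should be made, but the gap does not invalidate the design.

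**What to change.** Leave the dosing and stopping rules as they are.

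1. In 10.3, 12.5, 16.4 and the synopsis, separate discontinuation of the tracer from withdrawal from follow-up. Participants whose dosing ends after a SAR or severe AR then remain in the trial for safety data collection unless they choose to leave. Correct the section reference in 10.3.
2. Reconcile these passages with the abnormal-SST text in 12.5, 12.7 and the synopsis, so that one rule applies when the abnormal SST is the reaction. Add to 12.6 and 12.7 a branch for a patient with a normal SST and no second scan. The existing end conditions are written for adrenal dysfunction, so the investigators should set the end-of-follow-up condition for other reactions.
3. In 16.5, state that safety is reported as observed, by first and second administration, with the number actually dosed as denominator and the reasons why any second dose was not given. State that missing-at-random methods are not applied to safety outcomes.

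The cost is protocol wording and follow-up of at most a few patients by existing staff. The sample size does not change.

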16.5 Procedure to account for missing or spurious data

For participants who wish to withdraw entirely from the study, existing data acquired to the point of withdrawal will be included in the final study analysis, with missing data handled according to standard missing data methods, including missing-at-random methods.

16.6 Economic evaluation

No economic evaluation is planned.

16.7 Definition of the end of the trial

The end of trial will be the date of the last patient's last follow up visit.

17 Data handling and record keeping

17.1 Case Report Form (CRF)

All data will be transferred into a CRF which will be link-anonymised. All trial data in the CRF will be extracted from and be consistent with the relevant source documents. The CRFs will be completed, dated and signed by the investigator or designee in a timely manner. It remains the responsibility of the investigator for the timing, completeness, legibility and accuracy of the CRF pages. The CRF will be accessible to trial coordinators, data managers, the investigators, Clinical Trial Monitors, Auditors and Inspectors as required.

All CRF pages will be clear, legible and completed in black ink. Any errors will be crossed with a single stroke so that the original entry can still be seen. Corrections will be inserted and the change dated and initialled by the investigator or designee. If it is not clear why the change has been made, an explanation will be written next to the change. Typing correction fluid will not be used.

17.2 Source Data

To enable peer review, monitoring, audit and/or inspection the investigator agrees to keep records of all participating participants (sufficient information to link records e.g., CRF, hospital records and samples), all original signed informed consent forms and copies of the CRF pages.

17.3 Data Protection & Participant Confidentiality

All investigators and trial site staff involved in this trial will comply with the requirements of the General Data Protection Regulation (GDPR), the Data Protection Act 2018 and Trust Policy with regards to the collection, storage, processing, transfer and disclosure of personal information and will uphold the Act's core principles.

18 Independent Data Monitoring Committee

A single independent Data Monitoring Committee will oversee the trial and will be formed as follows:

- 1st DMC Member (Endocrinologist)
- 2nd DMC Member (Endocrinologist)
- 3rd DMC Member (Nuclear Medicine Physician)
- 4th DMC Member (Early Phase Clinical Trialist)
- Sponsor Representative (non-voting)

19 Ethical & Regulatory considerations

19.1 Ethical committee review

Before the start of the trial or implementation of any amendment we will obtain approval of the trial protocol, protocol amendments, informed consent forms and other relevant documents e.g., advertisements and GP information letters if applicable from the REC. All correspondence with the REC will be retained in the Trial Master File/Investigator Site File.

Annual reports will be submitted to the REC in accordance with national requirements. It will be the Chief Investigator's responsibility to produce the annual reports as required.

19.2 Regulatory Compliance

The trial will not commence until a Clinical Trial Authorisation (CTA) is obtained from the MHRA. The protocol and trial conduct will comply with the Medicines for Human Use (Clinical Trials) Regulations 2004 and any relevant amendments.

Development Safety Update Reports (DSURs) will be submitted to the MHRA in accordance with national requirements. It is the Chief Investigators responsibility to produce the annual reports as required.

19.3 Protocol Amendments

Protocol amendments will be reviewed and agreement received from the Sponsor for all proposed amendments prior to submission to the HRA, REC and/or MHRA.

The only circumstance in which an amendment may be initiated prior to HRA, REC and/or MHRA approval is where the change is necessary to eliminate apparent, immediate risks to the participants (Urgent Safety Measures). In this case, accrual of new participants will be halted until the HRA, REC and/or MHRA approval has been obtained.

19.4 Peer Review

The review was performed by the Research Advisory Committee at Cambridge University Hospitals NHS Foundation Trust. The Committee provide independent peer review for proposed studies that will be sponsored solely by the Trust or jointly with the University of Cambridge. To maintain the independence of the committee all reviews are undertaken in a confidential manner.

19.5 Declaration of Helsinki and Good Clinical Practice

The trial will be performed in accordance with the spirit and the letter of the declaration of Helsinki, the conditions and principles of Good Clinical Practice, the protocol and applicable local regulatory requirements and laws.

19.6 GCP Training

All trial staff will hold evidence of appropriate GCP training or undergo GCP training prior to undertaking any responsibilities on this trial. This training should be updated every 2 years or in accordance with the host Trust's policy.

20 Sponsorship, Financial and Insurance

The trial is sponsored by Cambridge University Hospitals NHS Foundation Trust and University of Cambridge. The trial will be funded by a UK Medical Research Council grant award to [name], [name], [name], [name] and [name] (Reference MR/P01710X/1).

Cambridge University Hospitals NHS Foundation Trust, as a member of the NHS Clinical Negligence Scheme for Trusts, will accept full financial liability for harm caused to participants in the clinical trial caused through the negligence of its employees and honorary contract holders. The University of Cambridge will arrange insurance for

negligent harm caused as a result of protocol design and for non-negligent harm arising through participation in the clinical trial.

Participants will be reimbursed for their time on the trial. They will be paid £250 upon completion of all trial visits. Participants who fail screening will be paid £50 in recognition of their time. Participants will also be reimbursed for reasonable travel costs.

21 Monitoring, Audit & Inspection

The investigator will make all trial documentation and related records available should an MHRA Inspection occur. Should a monitoring visit or audit be requested, the investigator will make the trial documentation and source data available to the Sponsor's representative. All participant data will be handled and treated confidentially.

The Sponsor's monitoring frequency will be determined by an initial risk assessment performed prior to the start of the trial. A detailed monitoring plan will be generated detailing the frequency and scope of the monitoring for the trial. Throughout the course of the trial, the risk assessment will be reviewed and the monitoring frequency adjusted as necessary.

22 Protocol Compliance and Breaches of GCP

Prospective, planned deviations or waivers to the protocol will not be allowed under the UK regulations on Clinical Trials and will not be used.

Protocol deviations, non-compliances, or breaches are departures from the approved protocol. They can happen at any time, but are not planned. They must be adequately documented on the relevant forms and reported to the Chief Investigator and Sponsor immediately.

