discontinued as a result of a SAR or a severe non-serious AR will be withdrawn from the trial

[figure not shown]
 Re-initiation of the trial can only be considered after MHRA approval via a substantial amendment. Any concurrently active participants will be re-consented before further IMP doses are administered, and all completed participants will be informed of the SAR or severe non-serious ARs.

[figure not shown]
Finally, if there is no demonstrable [¹⁸F]CETO uptake into human adrenal tissue in the first 4 participants (either healthy volunteers and/or patients), the trial will be halted and the DMC will be asked to consider if the trial should be stopped.

Criteria for withdrawal of participants

- A participant can decide to withdraw from the trial at any point without further explanation
- A participant can be withdrawn from the trial at the Investigator's discretion, as a result of safety considerations (e.g. an adverse event regardless of relation to the IMP) or protocol violation (e.g. failure to return for visits).
- Withdrawal from the trial will also occur in the event of participant pregnancy.
- Healthy volunteers will be withdrawn from the trial in the event that they are taking medication at the point of [¹⁸F]CETO administration.

6 Trial Flow Chart

7 Introduction

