- Adrenal function returns to baseline, as determined by follow-up SST.
- Participant/patient remains clinically stable, and where further follow-up can be managed safely in the outpatient setting.
- An alternative cause for the adrenal dysfunction is identified.
- Participant/patient is lost to follow-up.

Upon which their involvement in the trial will end.

Repeat PET-CT (Patients only)

Any patient who had an abnormal short synacthen test following the first scan will not be eligible to undergo the second scan. Eligible patients will undergo a second PET-CT scan (with dexamethasone pre-treatment) at ≥7 days after the initial scan

Prior to undertaking the second scan, the following assessments will be performed:

- Photo ID check
- Review of Dexamethasone medication diary
- Repeat urine pregnancy test for women of childbearing potential
- Blood tests:
 - FBC
 - U&Es, bicarbonate
 - LFTs
 - Direct Renin Concentration (DRC)
 - Plasma Aldosterone Concentration (PAC)
 - Adrenocorticotropic Hormone

Patients who fail to demonstrate 100% self-administration of dexamethasone in accordance with instructions provided by the trial team, assessed by review of the Dexamethasone medication diary, will not be able to proceed to a repeat PET-CT scan.

As no abnormal findings were recorded for these patients following the first scan, patients will only be observed for up to 4 hours in the PET-CT Unit after completion of the second scan. They will then be discharged by a clinical member of the research team with no requirement for admission to the CLRF or an additional SST.

Ongoing Safety Review

The safety data and PET-CT data will be reviewed by the Data Monitoring Committee (DMC) following injections of [¹⁸F]CETO in the first 3 participants to provide an initial evaluation of [¹⁸F]CETO safety and confirm the trial is able to proceed.

Furthermore, automatic trial stopping criteria will be met if a single participant experiences any serious adverse reaction (SAR, i.e. a serious adverse event considered at least possibly related to the IMP administration). Stopping criteria will additionally apply if any severe non-serious adverse reactions (ARs) develop in two participants, independent of whether or not these are within the same system-organ-class. The following will then occur:

- The trial will be halted via a substantial amendment to the MHRA.
- No further dosing or recruitment will be undertaken

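### Section 20 ties the £250 to completing every visit and is silent on early stopping, which gives the 6 patients a reason not to report a missed dexamethasone dose or a symptom between scans

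*Protocol*

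**What the plan says.** - **Payment (section 20).** "They will be paid £250 upon completion of all trial visits". The next sentence reads: "Participants who fail screening will be paid £50 in recognition of their time". Reasonable travel costs are also met. No sum is given for a participant who passes screening and then leaves or is stopped.
- **Dexamethasone diary (section 12.5, repeat PET-CT).** "Patients who fail to demonstrate 100% self-administration of dexamethasone" as instructed cannot go on to the second scan, and this is "assessed by review of the Dexamethasone medication diary". The course is 12 doses over three days, taken by the patient before the repeat scan.
- **Adverse events (section 5, criteria for withdrawal).** The investigator may withdraw a participant "as a result of safety considerations (e.g. an adverse event regardless of relation to the IMP" or not. Section 10.3 adds: "Any participants who have their dosing discontinued will be withdrawn from the trial".
- **Timing.** Section 9.4 puts the repeat scan at least 7 days after the first. The schedule in section 12.6 marks adverse event assessments on the scan day, at the SST follow-up visit if one is needed, and on the repeat scan day. Section 13.4 has events recorded from consent onwards.
- **Healthy volunteers.** They receive one dose (section 11.1.1.5). Section 10.3 states: "Healthy volunteers will be withdrawn from the trial in the event that they are taking medication" when the tracer is given.

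**The concern.** Section 20 presents the money as reimbursement for time, but ties it to finishing rather than to time given. Some of the facts that can prevent a patient from finishing are known to the team mainly because the patient reports them. Read as written, a truthful diary entry, or a truthful account of a symptom at home, can put the £250 at risk, while silence does not.

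Two results depend on those reports. The frequency of adverse events is the first component of the primary outcome (section 9.6.1), in an open-label first-in-human trial with 6 patients. The assessment of whether dexamethasone improves signal over background (section 7.3) assumes that the intake was what the diary says. Any distortion would run one way: fewer events and better adherence than was the case.

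**Working it through.** There is no power, error-rate or payment calculation in the protocol to reproduce, so the check sets the payment term against the rules that can end visits early.

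**Step 1. Which reports can cost a visit?**

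| Report | Who | Consequence | Visits still to come | Independent check |
|---|---|---|---|---|
| Missed dexamethasone dose | 6 patients | Automatic: no repeat scan (12.5) | Repeat scan day | Partial: ACTH drawn before scan 2, but no ACTH criterion is set |
| Symptom between scans | 6 patients | Discretionary withdrawal (5, 10.3) | Repeat scan day | None for a symptom at home |
| Symptom after the single dose | 5 volunteers | Discretionary withdrawal | Rest of the stay; a later visit only if the SST is abnormal | Supervised to about 24 hours |
| Medicine at dosing | 5 volunteers | Automatic withdrawal (10.3) | Dosing and scan | Medicines verified with the GP after screening (12.3.1) |
| Vital signs, ECG, laboratory values, SST | All | Various | Various | Measured, so the participant cannot withhold them |

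Only the first two rows combine a self-report, a real consequence for a later visit and a weak check. Both concern patients only.

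**Step 2. The diary gate.** Doses: 4 a day × 3 days = 12. One missed dose: 11/12 = 91.7%, which is below 100%. The scan is then barred with no discretion. The diary is read on the repeat scan day, before the scan. The patient has therefore attended, but cannot complete the visit as scheduled.

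**Step 3. Size for adverse events.** One unreported event among the patients is 1/6 = 16.7 percentage points. Going further needs two quantities that the protocol does not give: p, the true chance that a patient has a symptom-based event between scans, and q, the chance that it is reported. As an illustration only, with events independent between patients, P(at least one reported among 6) = 1 − (1 − pq)^6:

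| Assumed p | q = 1 | q = 0.75 | q = 0.5 |
|---|---|---|---|
| 0.10 | 0.47 | 0.37 | 0.27 |
| 0.20 | 0.74 | 0.62 | 0.47 |
| 0.30 | 0.88 | 0.78 | 0.62 |

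If 0 of 6 report an event, the exact one-sided 95% upper bound on the reported rate is 1 − 0.05^(1/6) = 39.3%. Dividing by q gives the bound on the true rate: 39.3% for q = 1, 52.4% for q = 0.75 and 78.6% for q = 0.5. With 6 patients, modest under-reporting would weaken a clean result, but nothing in the protocol says that q is below 1.

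**Step 4. Cost ceiling.** 11 participants × £250 = £2,750, the same as if all 11 complete.

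**The case against.** The strongest reply is that forfeiture is read into a silence. Section 20 does not say that a withdrawn participant receives nothing, and part payment may be set out in the information sheet, which is not among the documents and needs ethics approval. The list of visits is also not fixed: the SST follow-up visit happens only if necessary, and section 12.7 treats a patient with an abnormal result after scan 1 as concluding participation after follow-up. Completing every visit required of that person is a fair reading. All of this stands, and it limits the point to what section 20 states and leaves open.

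The reply is also right that reporting an adverse event does not in itself end participation. Withdrawal is discretionary, medication to treat an event is allowed (section 11.1.1.10), and the automatic halt needs a serious adverse reaction or severe reactions in two participants. This makes the adverse event route the weaker one. It does not remove it, because a patient at home cannot know how the discretion will be used.

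A reader might infer more: that the safety data are mostly self-reported, that £250 hangs on honesty for all 11 participants, or that a dosed participant withdrawn for an adverse event is paid less than a screen failure. The documents do not support these. Much of the primary outcome is measured, under close supervision on the scan day. The 5 healthy volunteers have almost nothing left to lose after dosing, and their medicines are checked with the GP. The payment after withdrawal is not stated, so it cannot be compared with £50. The diary and the volunteers' medicines are also not safety outcomes, although the diary bears on how scan 2 is interpreted.

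What survives is that section 20 states a completion condition and does not deal with the early stops that the protocol itself creates. For the diary, the consequence is automatic.

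**Conclusion.** The point holds in a narrow form, as an inexpensive improvement that should be made. For the 6 patients, the payment term as written works against honest reporting in the dexamethasone diary and, less strongly, of symptom-based adverse events between scan 1 and scan 2. The likely direction is towards better apparent adherence and fewer reported events.

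The size is unknown. The 1/6 figure is the weight of one event, not an estimate of how many would go unreported, and the table in the working rests on assumed values of p and q. The conclusion assumes that section 20 is applied as written and that no other document promises payment to those stopped early. It does not extend to vital signs, ECG, laboratory values or SST, nor in any material way to the healthy volunteers after dosing.

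**What to change.** Restate section 20 as payment per visit attended, with instalments that add up to the same £250 for a volunteer's visits and for a patient's visits. State that nothing is lost when the trial team or a protocol rule ends participation early: an adverse event, an abnormal SST, an incomplete diary or a trial halt. Say how the conditional SST visit is treated, so that the total stays at £250. Make the information sheet agree, so that patients know before they start the diary that a truthful entry costs them nothing. The £50 for screen failures can stay. The diary rule, dosing and assessments are not touched.

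The cost is an amendment and a few sentences of wording. The ceiling stays at £2,750. The downside is that some participants who stop early are paid, including a patient whose incomplete diary rules out the second scan.
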